## 1. INTRODUCTION

There is clearly a well-established clinical need to accurately measure the hepatic vein pressure gradient (HVPG) (Garcia-Tsao 1985). Unfortunately, current techniques are either invasive, such as catheter based pressure transducers, which have to be introduced directly into the hepatic vasculature, or noninvasive but indirect and qualitative, such as using CT, MRI or ultrasound imaging to diagnose liver cirrhosis (Kudo et al. 2008). However, the diagnostic accuracy of CT, MRI and ultrasound for grading cirrhosis into 3 categories (chronic hepatitis, cirrhosis and pre-cirrhosis) was only between 64 and 70% in a recent multi-center study (Kudo et al. 2008) and this is still only a very indirect measure of HVPG.

Our group has proposed and patented a novel and innovative technique called subharmonic-aided pressure estimation (SHAPE) for noninvasive pressure measurements (Forsberg et al. 2005; Shi et al. 1999; 2001). We have shown hydrostatic pressure can be measured through variations of the subharmonic amplitude of ultrasound contrast agents during insonation. Our group has just completed a first-in-humans clinical trial of SHAPE in 45 patients with chronic liver disease supported by RC1 DK087365 [Eisenbrey et al. 2013]. The SHAPE gradient between the portal and hepatic veins was in good overall agreement with the HVPG ( $R = 0.82$ ) indicating SHAPE may be a useful tool for the diagnosis of portal hypertension. This project will serve as a large clinical trial to further develop SHAPE and to employ this method to conduct a large scale human clinical trial to conclusively establish the accuracy of SHAPE for the assessment of portal hypertension.

### 1.1 Background

Portal hypertension is defined as an increase in the pressure gradient between the portal vein and hepatic veins or the inferior vena cava (IVC) exceeding 5 mmHg (Sanyal et al. 2008). Cirrhosis (prevalence of 2-10%) accounts for at least 90% of cases of portal hypertension in the developed world. From a pathophysiological perspective, the increase in portal venous pressure results from a sequence of events that begins with an increase in resistance to portal outflow, into the liver (Navarro et al. 2007). This is the result of two factors; architectural distortion of the liver parenchyma, as occurs in the accumulation of

fibrosis, and vasoconstriction of the hepatic microcirculation. The rise in portal pressure is largely asymptomatic until the body mounts a homeostatic response to systemic arterial vasodilatation. Specifically, systemic vasodilatation yields predictable physiological consequences, including systemic arterial hypotension, retention of salt and water and the formation of ascites, and renal insufficiency. In addition, up to 90% of the portal flow can be diverted into the systemic circulation through portosystemic collaterals (Sanyal et al. 2008).

Cirrhosis due to most causes, without the clinical manifestations of portal hypertension, has a small effect on mortality. However, it is the manifestations of portal hypertension which greatly impact survival. Common complications of portal hypertension include gastroesophageal varices, ascites, and portosystemic encephalopathy. Patients who develop ascites have a 50% two year mortality and those who develop spontaneous infection of the ascites fluid carry a 70% one year mortality. Patients with cirrhosis have a 5-10% yearly incidence of gastroesophageal variceal formation, and a 4-15% yearly incidence of bleeding, with larger varices having a greater risk for bleeding (D'Amico et al. 2006). Although the mortality associated with each bleeding event has fallen significantly due to endoscopic, pharmacological, and clinical care interventions, each bleeding episode continues to carry up to a 20% risk of death (D'Amico et al. 2006; Navarro et al. 2007; Sanyal et al. 2008).

In patients with chronic liver disease, transcatheter portal pressure measurement represents the “gold standard”, albeit indirect, for assessment of portal hypertension. The wedge hepatic venous pressure (WHVP) reflects values of portal venous pressure in cirrhosis (Sanyal et al. 2008). Another useful parameter is the gradient between the portal vein and the hepatic vein pressure, the hepatic vein pressure gradient (HVPG). The value of HVPG in assessing and monitoring several of the complications of portal hypertension is well established (D'Amico et al. 2006; Sanyal et al. 2008). It has also been found that an HVPG above 10 mmHg predicts the presence of varices, while an HVPG of 12 mmHg or more is required for varices to bleed (Garcia-Tsao 1985).

Variceal hemorrhage represents one of the most dramatic and immediately life threatening complications of portal hypertension and while the mortality rate has declined over the last decade it still ranges from 15 to 20% (Sanyal et al. 2008). Clinical management depends upon preventing an initial bleed when varices are present, intervening to stop active bleeding, and providing measures to prevent repeat bleeding. A sustained reduction in the HVPG to below 12 mmHg is the best predictor of successful reduction in the risk of bleeding with non-selective  $\beta$ -blockers. Likewise, a reduction in the risk of re-bleeding from varices is associated with a reduction in the HVPG of more than 20% from baseline or to less than 12 mmHg. Finally, the HVPG has been evaluated as a prognostic marker for disease progression, survival and mortality (Kalambokis et al. 2007). Most studies found that the HVPG, when added to other measures such as the Child Pugh or MELD scores, increased the ability to predict survival.

Consequently, our group has proposed and patented a novel and innovative technique called subharmonic-aided pressure estimation (SHAPE) for noninvasive pressure measurements (Forsberg et al. 2005; Shi et al. 1999; 2001). An accurate marker for portal hypertension would impact literally millions of Americans with liver disease. Such a marker could be used to predict the presence of portal hypertension and its complications (in particular varices) and might also be used to predict morbidity and mortality. Moreover, the value of HVPG measurements in the management of hepatocellular cancer (HCC) has been demonstrated. The noninvasive and accurate measurement of HVPG would also be clinically useful for trans-jugular intrahepatic portosystemic shunt (TIPS) procedures. TIPS are frequently performed for patients with intractable ascites not responding to medications or variceal bleeding which does not respond to pharmacological or endoscopic means. Patients with suspected variceal bleeding routinely undergo ultrasound examination to evaluate patency of the portal venous branches and determine whether TIPS placement is feasible. Getting a reliable estimate of HVPG in these patients with SHAPE would expedite therapy. SHAPE may also assist in the evaluation of ultrasound findings at TIPS follow-up studies, which can be technically challenging.

The proposed agent for the current study, Sonazoid® (GE Healthcare, Oslo, Norway), is a sterile non-pyrogenic suspension of lipid stabilized perfluorobutane microbubbles for contrast-enhancement, with a median diameter between 2.4 and 3.5  $\mu\text{m}$  (Forsberg et al. 2008). Previous *in vitro* results have shown that Sonazoid is superior for SHAPE measurements relative to other ultrasound contrast agents (Halldorsdottir et al. 2011). The FDA has yet to approve Sonazoid for human use in this country. Consequently, we intend to apply to the FDA for an investigator initiated IND to cover the use of Sonazoid in patients undergoing a trans-jugular liver biopsy. It should be pointed out that the safety of Sonazoid has already been established in numerous animal studies and in human studies for the evaluation of the liver and heart both in this country and in Europe (Landmark et al. 2008). Sonazoid has been approved for use in patients with liver lesions in Japan and has been marketed in that country since early 2007 and more recently in South Korea (Bouakaz et al. 2007; Jang et al. 2013). Finally, no adverse reactions attributable to contrast agent infusions were observed in our pilot study (Eisenbrey et al. 2013).

#### Sonazoid Clinical Safety

Sonazoid was administered in clinical trials in 1699 patients. In these patients 404 (23.8%) reported at least one adverse event, while 12 of 62 (19.4%) of patients receiving a placebo reported adverse events.

Forty-three (2.5 %, 43/1699) subjects experienced serious adverse events, including 13 deaths. None of these events were considered by the investigators to be related to Sonazoid. All the serious adverse events were considered to be caused by the underlying disease or related treatment. In addition, there were no clinically significant trends in laboratory tests, vital signs, ECGs, or physical examination findings.

The most commonly noted adverse events were headache (3.6%, 62/1699), chest pain (2.3%, 39/1699), abdominal pain (1.5%, 25/1699), diarrhea (1.5%, 25/1699), and nausea (1.6%, 28/1699). The majority of adverse events were mild to moderate in severity (92.6%, 652/704).

Table 1.

Selected Adverse Events Reported in  $\geq 0.5\%$  of the Subjects who Received Sonazoid in Controlled Clinical Studies (% of 1699)

No. of Patients Exposed to Sonazoid	1699
No. of Patients Reporting an Adverse Event	404 (23.8%)
Application Site Disorders	9 (0.5%)
Body as a Whole	91 (5.4%)
Back Pain	10 (0.6%)
Chest Pain	39 (2.3%)
Cardiovascular System, General	45 (2.6%)
ECG Abnormal Specific	15 (0.9%)
Hypotension	9 (0.5%)
Nervous	94 (5.5%)
Dizziness	18 (1.1%)
Headache	62 (3.6%)
Gastrointestinal	126 (7.4%)
Abdominal Pain	25 (1.5%)
Diarrhea	25 (1.5%)
Nausea	28 (1.6%)
Vomiting	21 (1.2%)
Heart Rate & Rhythm	55 (3.2%)
Liver and Biliary System	22 (1.3%)
SGOT/AST increased	9 (0.5%)
Metabolic & Nutritional	42 (2.5%)
Increased LDH	17 (1.0%)
Musculo-Skeletal System	18 (1.1%)
Myo-, Endo-, Pericardial & Valve	29 (1.7%)
Angina Pectoris	14 (0.8%)
Platelet, Bleeding & Clotting	21 (1.2%)
Psychiatric	19 (1.1%)
Respiratory System	58 (3.4%)
Dyspnoea	19 (1.1%)
Skin & Appendages	18 (1.1%)
Urinary System	31 (1.8%)
Albuminuria	17 (1.0%)
White Cell & RES	9 (0.5%)

Additional information concerning pre-clinical and clinical experience with Sonazoid, including the dosing levels and reported subject complaints, can be found in the Sonazoid investigational drug brochure (Version 7, October 4th 2002).

## 1.2 Rationale

The quantitative aspect of this project is based on the assumption that the magnitude of subharmonic signals from insonated contrast agents depend on the hydrostatic pressure of the surrounding media. SHAPE estimates internal pressure variations by transmitting at one frequency, receiving at its subharmonic frequency and then monitoring the subharmonic amplitude variations from the contrast bubbles. The optimal sensitivity for SHAPE was determined *in vitro* to be at a transmit frequency of 2.5 MHz (i.e., receiving at 1.25 MHz) at a 0.35 MPa acoustic pressure using the contrast agent Sonazoid (GE Healthcare, Oslo, Norway), which declined approximately 14.4 dB over a 0 to 186 mmHg pressure range.

We propose a large clinical trial at two sites to further develop SHAPE and to employ this method to conduct a large scale human clinical trial to conclusively establish the accuracy of SHAPE for the assessment of portal hypertension. The purpose of this study is to evaluate if SHAPE measurements may be used as a first qualitative screening modality for determining the presence of portal hypertension in patients undergoing a transjugular liver biopsy and determine if SHAPE measurements may be used to monitor disease progression or treatment response for patients diagnosed with portal hypertension.

## 2. TRIAL OBJECTIVES

Trial Objectives: The primary objectives of this trial are:

- Evaluate the use of *in vivo* subharmonic aided pressure estimation (SHAPE) as a first qualitative screening modality for determining the presence of portal hypertension in patients undergoing a transjugular liver biopsy compared to catheter based pressure measurements (as the reference standard)
- Determine if SHAPE measurements can provide a quantitative, noninvasive measurement of hepatic venous pressure gradient (HVPG) to monitor disease progression or treatment response in patients identified with portal hypertension by comparing the results to repeat biopsies and/or clinical outcomes.

## 3. TRIAL DESIGN

This is an open-label, non-randomized trial that will be conducted at two clinical sites, Thomas Jefferson

University (TJU) and the Hospital of the University of Pennsylvania (HUP). Enrolled patients undergoing trans-jugular liver biopsy will receive a continuous infusion of Sonazoid® (GE Healthcare, Oslo, Norway) co-infused with 0.9% NaCl solution over a 5-10 minute time period using the setup and infusion rates described in GE Healthcare (GEHC) Protocol Supplement provided in Appendix B. Ultrasound imaging will be performed using a Logiq 9 scanner with a 4C transducer (GE Healthcare, Milwaukee, WI) and the SHAPE algorithm will be used to measure pressure values in the hepatic and portal veins. Data will be stored on a PC and compared to pressure-catheter measurements, which are taken as part of the standard of care for all patients undergoing a trans-jugular biopsy. Subjects identified in the initial examination as having portal hypertension (by HVPG results) will be monitored by SHAPE for up to 18 months. These subjects typically have surveillance CT or MRI scans every 6 months to check for liver cancer and at those times a repeat SHAPE examination will be performed (ideally within 2 weeks). Any repeat transjugular biopsies performed in this population will also trigger a repeat SHAPE study. Results of blood test evaluations (performed every 3 months in this population), medication, concomitant imaging study or procedure (including endoscopies) done as standard of care will be noted. The end point for this part of the study will be any one new complication (e.g., liver cancer) or a marked worsening in any complication, liver transplantation, death, or the end of the clinical trial participation (up to 18 months). On an average, these patients will be monitored three times during the course of this clinical trial.

A full demographic profile, known drug allergies or intolerances, and review of the subject's medical/surgical history will be recorded. If the subject is a woman of childbearing potential, she will have a urine pregnancy test (the results of which will be made available to the subject prior to study initiation).

### 3.1 Trial Duration

Individual participation in this trial will be limited to ultrasound imaging studies within the two hour period following a trans-jugular liver biopsy (during which their hepatic wedge pressure will be measured

with a pressure catheter as part of the standard of care at TJU and HUP). Patients are monitored for two hours (1 hour post Sonazoid injection). The entire ultrasound imaging protocol will require approximately one hour. Subjects identified in the initial examination as having portal hypertension (by HVPG results) will be monitored by SHAPE for up to 18 months. These subjects typically have surveillance CT or MRI scans every 6 months to check for liver cancer and at those times a repeat SHAPE examination will be performed. Any repeat trans-jugular biopsies performed in this population will also trigger a repeat SHAPE study. Moreover, these patients will have a complete blood test every 3 months and these clinical variables (platelets, albumin, MELD, etc.) as well as any medication will be recorded. Finally, most subjects with portal hypertension will undergo an endoscopy examination every 1 to 2 years [de Franchis 2005; Merkel et al. 2004]. Results of any concomitant imaging study or procedure (including endoscopies) will be noted. The end point for this part of the study will be any one new complication (e.g., liver cancer) or a marked worsening in any complication (e.g., MELD scores), liver transplantation, death, or the end of this clinical trial (after 3 years). On an average, these patients will be monitored three times during the course of this clinical trial. The time to reach the end point will be noted if a new complication or a marked worsening in any complication occurs.

Subject recruitment is expected to last 3 years (April, 2014 – January, 2017). This includes monitoring disease progression and/or treatment response. Analysis and publication of results are expected to take an additional 2 months (January– March, 2017). Volunteer Registry Database forms will be submitted to the National Institute of Health’s Office of Regulatory Compliance and Quality at the completion of the research study.

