## 6.7 End-of-Treatment and End-of-Trial Evaluations

### 6.7.1 Discontinuation of Subjects

Subjects will be free to discontinue trial participation at any time. The investigator will also discontinue any subject from the trial if, in the investigator's opinion, it is not safe for the subject to continue. The date the subject is withdrawn from a treatment and/or from the trial and the reason for discontinuation will be recorded on the CRF. For portal hypertension patients that will be monitored by SHAPE for up to 18 months, the end point will be any one new complication (e.g., liver cancer) or a marked worsening in any complication (e.g., MELD scores) or the end of their clinical trial participation (up to 18 months). The time to reach the end point will be noted if a new complication or a marked worsening in any complication occurs. The time to reach the end point will be noted.

Trial participation will be considered completed if the subject has met all of the following trial

requirements:

- Has received at least one infusion of Sonazoid
- Has undergone the complete ultrasound imaging study as described in this protocol

If a subject's participation in the trial is interrupted for any reason (e.g., because of an AE or if the subject is lost to follow-up) and the subject has met the criteria described above for completing the trial, the subject's trial participation will be considered completed. If a subject's trial participation is interrupted for any reason by the subject's or investigator's choice and the subject has not met all of the criteria listed above, then the subject will be considered a discontinued subject.

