### 7.2 Statistical Analyses

#### 7.2.1 Hypotheses

$H_1$ : Can patients with HVPG of 10 mmHg or greater be identified using SHAPE? The fundamental hypothesis is that a sensitivity of 89% and a specificity of 81 % can be achieved by using SHAPE measurements to identify patients with HVPGs of 10 mmHg or greater.

H2: A correlation coefficient of 0.82 will be achieved between in vivo SHAPE and HVPG measurements.

H3: A correlation coefficients above 0.90 will be achieved between SHAPE and repeat HVPG results.

H4: SHAPE will significantly differentiate responders from non-responders using clinical outcomes as the reference standard.

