### 7.2.2 Analysis of Results

The findings of SHAPE will be correlated to the invasive catheter based measurements of portal vein blood pressure (i.e., HVPG) using least squares, multiple linear regression analysis with robust standard errors. Receiver operating characteristic (ROC) curves will be computed using a continuous scale with HVPG cutoff levels of 10 and 12 mmHg. The optimal operating point (OOP) will be determined as the point closest to '0,1' on the ROC curve (representing 100% sensitivity and 100% specificity). All clinical variables (e.g., concomitant imaging results, presence of cancer or ascites, blood tests, fibrosis and MELD scores etc.) will also be compared to the SHAPE values. When both types of variables are ordinal or continuous, correlations will be calculated. When one type of variable is nominal and one continuous non-parametric rank order tests such as Mann-Whitney U-tests or Kruskal-Wallis tests will be performed [Rosner 1990]. All of the statistical analyses proposed for the human clinical trial will be repeated split by racial and ethnic groups to determine if clinically important race/ethnicity differences exist in the ability of SHAPE to diagnose portal hypertension.

All analyses and computations will be performed using NCSS/PASS 2008 and Stata 12.0 (Stata Corporation, College Station, TX), while the study database will be designed and implemented in Filemaker Pro 10.0 (Filemaker Inc, Santa Clara, CA). This database will contain all patient information (except names and other identifiers), including results of biopsies, HVPG and SHAPE measurements as well as the clinical variables.

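### H4 has no assigned analysis, responder definition, time horizon or censoring rule, although follow-up is unequal by design and the sections disagree on end points and on which times are recorded

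*Combined protocol and SAP*

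**What the plan says.** H4 in section 7.2.1 reads: "SHAPE will significantly differentiate responders from non-responders using clinical outcomes as the reference standard". It belongs to the second primary objective in section 2, on monitoring progression or treatment response. No test, definition of a responder or time point is attached to it there or elsewhere.

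Section 7.2.2 gives a general rule for comparing clinical variables with SHAPE: "When one type of variable is nominal and one continuous non-parametric rank order tests such as Mann-Whitney U-tests or Kruskal-Wallis tests will be performed". Where both variables are ordinal or continuous, correlations are calculated. No censoring rule and no survival method appears in the document.

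On follow-up, section 3.1 says that patients with portal hypertension "will be monitored by SHAPE for up to 18 months". It also says: "Subject recruitment is expected to last 3 years (April, 2014 – January, 2017). This includes monitoring disease progression and/or treatment response". After that, "Analysis and publication of results are expected to take an additional 2 months".

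On recording of times, the Synopsis (Trial Design) and section 3.1 both say: "The time to reach the end point will be noted if a new complication or a marked worsening in any complication occurs". Section 6.7.1 repeats that sentence and then adds one without the condition.

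**The concern.** H4 asks whether SHAPE separates patients who do well from those who do not. Whether a patient is seen to reach an end point depends partly on how long that patient is watched, and here this ranges from almost nothing to 18 months. An analysis that ignores observation time mixes patients who were event-free for 18 months with patients who were hardly observed. That dilutes the contrast and costs power. If observation time is also related to SHAPE, through selective loss or a drift in SHAPE values over enrolment, it can produce a difference that is not real.

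The remedy needs an exit date and status for every monitored patient. The sections do not agree on whether those dates are collected, and a last-contact date that was not recorded may be impossible to recover at analysis.

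**Working it through.** **1. The plan's own figures.** There is none for H4. Section 7.2.3 sizes the trial on aim 1 and, separately, on the SHAPE-HVPG correlation. The figure that bears on follow-up is the recruitment rate: 300 / ((85 + 100) × 3) = 300/555 = 54.05%, which reproduces the stated 54%. It relies on accrual through all three years.

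**2. Could all patients be enrolled early enough for 18 months?** The dates give about 33 months; the stated duration gives 36. Entry would have to end by month 33 − 18 = 15, or 36 − 18 = 18. Procedures available by then are 185 × 15/12 = 231, or 185 × 18/12 = 277.5. Both are below 300 even if every patient consents, so some of the 300 must enter too late for 18 months.

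**3. Distribution of follow-up.** Assume even accrual over T months, with follow-up = min(18, T − entry month).

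| | T = 33 | T = 36 |
|---|---|---|
| under 18 months (18/T) | 55% | 50% |
| under 12 months (12/T) | 36% | 33% |
| under 6 months (6/T) | 18% | 17% |
| mean, [(T − 18)·18 + 18·9]/T | 13.1 | 13.5 |

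**4. Events not seen if patients are classed simply as event yes or no.** Assume exponential event times with 18-month risk p and λ = −ln(1 − p)/18. The observed proportion is [(T − 18)·p + (18 − p/λ)]/T. For p = 0.30 and T = 33: λ = 0.0198, 18 − p/λ = 2.86, and the observed proportion is (15 × 0.30 + 2.86)/33 = 0.223. Events missed: 1 − 0.223/0.30 = 26%. Share of the apparently event-free who would have had an event by 18 months: (0.30 − 0.223)/(1 − 0.223) = 10%. Over p = 10 to 50% and T = 33 or 36, these run from 22 to 27% and from 3 to 20%.

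**5. Power.** Simulation, T = 33, hazard ratio 1.5 per SD of SHAPE, 600 replicates per row. The number monitored, the risk and the hazard ratio are assumptions; the documents give none.

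| Patients | 18-month risk | Rank test, event yes/no | Cox with censoring | Rank test if all had 18 months |
|---|---|---|---|---|
| 100 | 20% | 32.5% | 33.8% | 41.5% |
| 100 | 40% | 50.0% | 55.5% | 67.7% |
| 150 | 20% | 44.2% | 50.8% | 58.3% |
| 150 | 40% | 69.0% | 76.0% | 83.8% |

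Simulation error is up to √(0.5 × 0.5/600) = 2 points per entry. A repeat on the same inputs gave 33% against 35% at the low end and 71% against 78% at the high end, so the loss is about 2 to 7 points.

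**6. Type I error.** No true effect, 120 patients, 30% risk, 1,000 replicates.

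| Situation | Rank test | Cox |
|---|---|---|
| follow-up unrelated to SHAPE | 4.3% | 4.6% |
| 20% loss, loss hazard ratio 2 per SD | 6.7% | 5.5% |
| 40% loss, loss hazard ratio 2 per SD | 10.4% | 5.6% |
| SHAPE drifts 1 SD over accrual | 8.9% | 5.4% |

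**7. The sections side by side.**

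| Section | Death and transplantation listed | Follow-up ends | Time recorded |
|---|---|---|---|
| Synopsis, Trial Design | yes | end of trial, 3 years | complication or worsening only |
| 3 | yes | end of participation, up to 18 months | not stated |
| 3.1 | yes | end of trial, 3 years | complication or worsening only |
| 6.7.1 | no | end of participation, up to 18 months | conditional sentence, then an unconditional one |

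All four list the end of the trial or of participation as an end point alongside clinical events. The Synopsis and section 3.1 also cap SHAPE monitoring at 18 months.

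**The case against.** A reader might infer that the plan compares event and non-event patients with rank tests, counts briefly watched patients as event-free, and turns lost patients into responders because "the subject's trial participation will be considered completed". The documents do not say this. H4 is given no test by name; section 7.2.2 states a general rule for clinical variables, and applying it to H4 is an inference. No section defines a responder or says how a patient with short follow-up is classified. Completion in section 6.7.1 is a participation status, reached after one infusion and one full imaging study. It is not an outcome or censoring rule.

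Nor can it be said that times are recorded only for some events. Section 6.7.1 has the unconditional sentence and requires the date and reason of withdrawal on the CRF. What stands is narrower: the sections conflict, and it is not clear that the withdrawal-date requirement reaches a lost patient who already counts as completed.

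The size is also modest. At 100 patients and 20% risk the two methods hardly differ. Much of the lost power comes from short follow-up itself, which Cox does not restore (76% against 84% in the last row of the power table). The documents give no evidence of a SHAPE drift or of selective loss. Finally, Cox is not the only valid choice: a fixed-horizon definition with a rule for incomplete follow-up would also serve. These points limit the claim, but H4 still has no stated analysis that allows for unequal follow-up.

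**Conclusion.** The point holds as a gap together with an inconsistency. H4 cannot be analysed from the plan as written, and the only listed method that fits ignores a length of follow-up that the trial's own calendar makes unequal. Under even accrual, 50 to 55% of monitored patients cannot reach 18 months. Using the rank test on event yes or no would cost about 2 to 7 percentage points of power against Cox, on the assumed hazard ratio, numbers and risks above. Its type I error stays nominal unless follow-up length is related to SHAPE; in the assumed cases of that kind it reached about 7 to 10%. The change should be made, because it is cheap now and missing exit dates may not be recoverable later.

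**What to change.** - Record, for every monitored patient, an end-point or last-contact date and a status: complication, worsening, transplantation, death, loss or closure.
- Reconcile the Synopsis, sections 3 and 3.1, and section 6.7.1 on the list of end points, on which times are recorded and on when follow-up ends. Treat the end of the trial or of participation as censoring, not as an outcome.
- Name the analysis for H4 in section 7.2.2: time to first end point, for example a Cox model on a pre-stated SHAPE measure such as baseline SHAPE, with Kaplan-Meier curves. Censor at loss or closure, and state whether death and transplantation count as events or as competing events.
- If a responder classification is kept, define it at a fixed horizon with a rule for patients whose follow-up stops short of it.

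The cost is one date and status field per patient, SAP wording and some added analysis. No extra visits are needed and no stated sample-size figure changes.
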